### 3.4.3 Supportive analyses

These analyses will not be provided, since the enrollment in the study was halted after only a few patients treated. See details in Section 4.

### 3.4.4 Sample size calculation

The sample size is determined based on the primary efficacy endpoint PFS.

Under the hypothesis in [Section 3.4.2](#), 23 PFS events are required for a one-sided type I error of  $\alpha = 0.05$  and 80% power to reject  $H_0$  when the true log hazard ratio is  $HR = 0.33$  using a

log-rank test. It is assumed the median PFS for placebo is 2 months and median PFS for LEE011 is 6 months. Under an exponential survival model, a 3-fold increase of PFS (or a 66.7% reduction in the hazard rate) is expected on treatment of LEE011 against placebo.

[REDACTED]

The expected study duration is approximately 24 months (completed study) (inflated by 3 months in order to take into account for a 15% drop-out rate).

The sample size calculation was performed using software package [EAST 5.4](#).

### **3.5 Efficacy evaluation (Secondary [REDACTED] Objectives)**

These analyses will not be provided, since the enrollment in the study was halted after only a few patients treated. See details in Section 4.

### **3.6 Safety evaluation**

The assessment of safety is based on the type of AEs and frequency of AEs as well as on the number of laboratory values that fall outside of pre-determined ranges (Common Toxicity Criteria [CTC] version 4.03 grading limits or normal ranges as appropriate).

The Safety set will be used for summaries and listings of all safety data in Section 14 of the CSR. Safety analyses will be performed per treatment received (see [Section 2.1.1.2](#)). The FAS will be used for Section 16 of the CSR, including for safety listings. These listings will be displayed per intended treatment as per all analyses performed on the FAS (see [Section 2.2](#)). Differences between treatment received and intended treatment, if any, will be provided in a listing.

The safety summary tables will include only assessments collected no later than 30 days after study treatment discontinuation. All safety assessments will be listed, and those collected later than 30 days after study treatment discontinuation will be flagged.

For patients who crossed over to LEE011, the placebo group will include all events before the date of first administration of LEE011 and will not include the 30 days are described above. While the LEE011 crossed over group will include all events after the date of first administration of LEE011 and will include the 30 days.

#### **3.6.1 Adverse event**

Adverse events are coded using the Medical Dictionary for Regulatory Activities (MedDRA) terminology. Although CTCAE version 4.03 grading is by definition a 5-point scale generally corresponding to mild, moderate, severe, life threatening and death, CTCAE grade 5 (death) will not be used since this information will be collected on the “End of Treatment”, “Study evaluation completion” or “Survival information” CRF pages.

Separate summaries and listing for adverse events (AEs) and serious AEs (SAEs) recorded during the study, and all death (on-treatment and post-treatment, with appropriate flag variable to identify on-treatment death) will be provided. Additional summaries and listing based on the relationship to study drug by treatment, study drug discontinuation, requiring dose adjustment or delay will be produced. Listing and summaries will be produced according to the following rules:

- Patients reporting and experiencing multiple occurrences of a specific AE will have occurrences listed but will be counted only once in the appropriate event category/class and according to the worst observed grade within summary tables.
- AEs will be summarized by presenting the number and percentage of patients having at least one AE, and having at least one AE in each primary system organ class and for each preferred. AE will be sorted by descending frequency or alphabetically (system organ class [SOC] and preferred term [PT]).
- An adverse event of special interest is a grouping of adverse events that are of scientific and medical concern specific to compound LEE011. These groupings are defined using MedDRA terms, SMQs (standardized MedDRA queries), HGLTs (high level group terms), HLT (high level terms) and PTs (preferred terms). Customized SMQs (Novartis MedDRA queries, NMQ) may also be used. A NMQ is a customized group of search terms which defines a medical concept for which there is no official SMQ available or the available SMQ does not completely fit the need. It may include a combination of single terms and/or an existing SMQ, narrow or broad. For each specified AESI, number and percentage of subjects with at least one event of the AESI occurring during on-treatment period will be summarized. Summaries of these AESIs will be provided by treatment, (specifying grade, SAE, relationship, leading to treatment discontinuation, leading to dose adjustment/interruption, fatal outcome, etc.). A listing of all grouping levels down to the MedDRA preferred terms used to define each AESI will be generated.

### **3.6.2 Deaths**

[figure not shown]
Summary of all deaths will be produced by treatment, system organ class and preferred term. All deaths will be listed for the FAS, on treatment deaths will be flagged.

[figure not shown]
### **3.6.3 Laboratory data**

Summary of notable hepatic laboratory values will be produced by treatment. Liver function test values will be listed. No other laboratory data will be analyzed.

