6.2 Dose modifications

6.2.1 Dose modification and dose delay

For patients who do not tolerate the protocol-specified dosing schedule, dose adjustments are permitted in order to allow the patient to continue the study drug. These changes must be recorded on the Dosage Administration Record eCRF. For patients undergoing a dose delay or reduction mid-cycle, upon restarting LEE011 during that cycle the, dosing should resume per the original cycle schedule. The planned 7-day break should begin on the originally planned date regardless of mid-cycle interruptions. Day 1 of subsequent cycles may be delayed if necessary to allow for toxicity resolution. If the study drug is delayed for more than 21 days due to drug toxicity, then study drug should be discontinued.

Severe or intolerable AEs may require dose reduction and/or interruption of study drug. Refer to Table 6-2 for guidance.

Table 6-2 Dose adjustments

Dose level	Daily dose	Frequency
*-2	200 mg	Daily (21 days), followed by one week break
*-1	400 mg	Daily (21 days), followed by one week break
1 (starting dose)	600 mg	Daily (21 days), followed by one week break

*Dose level-1 and -2 represent treatment doses for patients requiring a dose reduction from the starting dose level. No dose reduction below dose level -2 is permitted for this study.

[REDACTED]

Recommendations for dose reduction, interruption or discontinuation of study drug in the management of AEs are summarized in [Table 6-3](#). Clinical judgment of the treating physician and an individualized risk/benefit assessment should guide the management plan for each patient. A maximum of two study drug dose reductions (minimum dose is 200 mg) is allowed before study drug must be discontinued. Once a dose reduction has occurred, the dose level may not be re-escalated until the adverse event resolves to grade 1 and dose change has been authorized by the Novartis team.

Table 6-3 Study drug dose adjustment and management recommendation for hematological adverse reactions

[figure not shown]
Toxicity/Grade	Dose Adjustment and Management Recommendations
Thrombocytopenia	
Grade 1 ($\geq 75 \times 10^9/L$)	No dose adjustment required.
Grade 2 ($\geq 50 \times 10^9/L - < 75 \times 10^9/L$)	Dose interruption until recovery to grade ≤ 1 . Re-initiate study drug at the same dose.

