Grade 3 ($\geq 25 \times 10^9/L - < 50 \times 10^9/L$)	Dose interruption until recovery to grade ≤ 1 . Re-initiate study drug at the same dose level. If toxicity recurs at grade 3: temporary dose interruption until recovery to grade ≤ 1 and reduce study drug to the next lower dose level.
Grade 4 ($< 25 \times 10^9/L$)	Dose interruption until recovery to grade ≤ 1 . Re-initiate study drug at the next lower dose level. If toxicity recurs at grade 4: discontinue study drug.
Absolute neutrophil count (ANC)	
Grade 1 ($\geq 1.5 \times 10^9/L$)	No dose adjustment required.
Grade 2 ($\geq 1.0 - < 1.5 \times 10^9/L$)	No dose adjustment required.
Grade 3 ($\geq 0.5 - < 1.0 \times 10^9/L$)	Dose interruption until recovery to $\geq 1.0 \times 10^9/L$. Re-initiate study drug at the same dose level. If toxicity recurs at grade 3: temporary dose interruption until recovery to $\geq 1.0 \times 10^9/L$. If resolved in ≤ 7 days, then maintain dose level. If resolved in > 7 days, then reduce study drug dose to the next lower dose level.
Grade 4 ($< 0.5 \times 10^9/L$)	Dose interruption until recovery to $\geq 1.0 \times 10^9/L$. Re-initiate study drug at the next lower dose level. If toxicity recurs at grade 4: temporary dose interruption until recovery to $\geq 1.0 \times 10^9/L$ and reduce study drug at the next lower dose level.
Febrile neutropenia	
Grade 3 ANC $< 1.0 \times 10^9/L$ with a single temperature of $> 38.3 \text{ }^\circ\text{C}$ ($101 \text{ }^\circ\text{F}$) or a sustained temperature of $\geq 38 \text{ }^\circ\text{C}$ ($100.4 \text{ }^\circ\text{F}$) for more than one hour	Dose interruption until improvement of ANC $\geq 1.0 \times 10^9/L$ and no fever. Restart at the next lower dose level. If febrile neutropenia recurs, discontinue study drug.
Grade 4 Life-threatening consequences; urgent intervention indicated	Discontinue study drug
Anemia (Hemoglobin)	
Grade 1 ($\geq 10.0 - \text{LLN g/dL}$)	No dose adjustment required.
Grade 2 ($\geq 8.0 - < 10.0 \text{ g/dL}$)	No dose adjustment required.
Grade 3 ($< 8.0 \text{ g/dL}$)	Dose interruption until recovery to grade ≤ 2 .

Toxicity/Grade	Dose Adjustment and Management Recommendations
	Re-initiate study drug at the same dose.
Grade 4 Life-threatening consequences; urgent intervention indicated	Discontinue study drug.

Table 6-4 Study drug dose adjustment and management recommendation for hepatic toxicities

HEPATOTOXICITY (BILIRUBIN, SGPT/ALT, SGOT/AST)	

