8.1 Adverse events

8.1.1 Definitions and reporting

An adverse event (AE) is defined as the appearance of (or worsening of any pre-existing) undesirable sign(s), symptom(s), or medical condition(s) that occur after a patient's signed informed consent has been obtained.

Abnormal laboratory values or test results occurring after informed consent constitute adverse events only if they induce clinical signs or symptoms, are considered clinically significant, require therapy (e.g., hematologic abnormality that requires transfusion or hematological stem cell support), or require changes in study medication(s).

Adverse events that begin or worsen after informed consent should be recorded in the Adverse Events eCRF. Conditions that were already present at the time of informed consent should be recorded in the Medical History eCRF. Adverse event monitoring should be continued for at least 30 days (or 5 half-lives, whichever is longer) following the last dose of study treatment. Adverse events (including lab abnormalities that constitute AEs) should be described using a diagnosis whenever possible, rather than individual underlying signs and symptoms. When a clear diagnosis cannot be identified, each sign or symptom should be reported as a separate Adverse Event.

Adverse events will be assessed according to the Common Terminology Criteria for Adverse Events (CTCAE) version 4.03. If CTCAE grading does not exist for an adverse event, the severity of mild, moderate, severe, and life-threatening, corresponding to Grades 1 - 4, will be used. CTCAE Grade 5 (death) will not be used in this study; rather, information about deaths will be collected through a Death form.

The occurrence of adverse events should be sought by non-directive questioning of the patient during the screening process after signing informed consent and at each visit during the study. Adverse events also may be detected when they are volunteered by the patient during the screening process or between visits, or through physical examination, laboratory test, or other assessments. As far as possible, each adverse event should be evaluated to determine:

1. The severity grade (CTCAE grade 1-4)
2. Its duration start and end dates or Ongoing at End of Study
3. Its relationship to the study treatment (Reasonable possibility that AE is related: No, Yes)

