10.5.3.3 Laboratory abnormalities

For laboratory tests covered by the Common Terminology Criteria for Adverse Events (CTCAE) version 4.03 the study's biostatistical and reporting team will grade laboratory data accordingly. For laboratory tests covered by CTCAE, a Grade 0 will be assigned for all non-missing values not graded as 1 or higher. Grade 5 will not be used.

If the lower limits of normal ranges used in CTCAE definitions are missing, then they have to be replaced by clinical meaningful limit. For laboratory tests where grades are not defined by CTCAE, results will be graded by the low/normal/high classifications based on laboratory normal ranges.

The following by-treatment summaries will be generated separately for hematology, biochemistry and urinary laboratory tests:

- frequency table for newly occurring on-treatment CTCAE Grade 3 or 4 toxicities
- shift tables using CTCAE grades to compare baseline to the worst on-treatment value
- for laboratory tests where CTCAE grades are not defined, shift tables using the low/normal/high/(low and high) classification to compare baseline to the worst on-treatment value
- listing of all laboratory data with values flagged to show the corresponding CTCAE grades and the classifications relative to the laboratory normal ranges

In addition to the above mentioned tables and listings, [REDACTED]

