#### **4 Change to protocol specified analyses**

Since the enrollment in the study was halted after only a few patients treated (10 patients), only the outputs defined in the document “Guidelines for short, closeout CSRs” (released on the 17-Sept-2014) will be produced.

Therefore, the following analyses will not be performed:

- [Protocol Section 10.3.1 Study Treatment]: The actual dose, dose intensity, relative dose intensity and total daily doses of each agent will not be summarized or listed.
- [Protocol Section 10.3.2 Concomitant therapies]: Concomitant medications and significant non-drug therapies prior to and after the start of the study drug treatment will not be summarized or listed.
- [Protocol Section 10.3.3 Compliance]: The listing of patients with protocol deviations will be provided; no summary tables will be produced.
- [Protocol Section 10.4.2] The primary efficacy endpoint, PFS will not be analyzed. Log-rank test, HR estimates and related confidence interval and Kaplan-Meier estimates with confidence interval for median survival and survival probabilities will not be performed.
- [Protocol Section 10.5.2 Other secondary efficacy objectives]: BOR, ORR and DCR will not be summarized and corresponding confidence interval will not be produced. Kaplan-Meier plots for DOR will not be produced and the median DOR will not be estimated. Kaplan-Meier estimates for OS with confidence intervals will not be produce and OS rate and related confidence interval will not be performed. Listing of Overall response, time to progression time to onset and duration of overall response will not be provided. Waterfall plot will not be produced.
- [Protocol Section 10.5.3 Safety objectives]: Laboratory abnormalities, ECG, Cardiac Imaging and vital signs summary tables and listings will not be provided. Tolerability of the study drug will not be summarized and reason for dose interruption, dose reduction and dose change will not be listed by patient or summarized.
- [Redacted]
- [Redacted]
- [Redacted]

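### The close-out SAP drops all hematology output against its own retained text, and adverse-event tables replace it only in part

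*SAP*

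**What the plan says.** **Close-out SAP, what is removed.** Section 3.6.3 keeps a summary of notable hepatic values and a listing of liver function tests, then states "No other laboratory data will be analyzed". Section 4 says of the protocol 10.5.3 outputs: "Laboratory abnormalities, ECG, Cardiac Imaging and vital signs summary tables and listings will not be provided". The reason it gives begins "Since the enrollment in the study was halted after only a few patients treated (10 patients", and it points to a guideline for short close-out reports.

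**Close-out SAP, what is retained.** Section 3.6 still bases the safety assessment on AEs and on the "number of laboratory values that fall outside of pre-determined ranges", and says that every safety assessment will be listed. Section 3 still promises listings of all raw data. Table 1-1 still names changes in laboratory values among the safety endpoints. Section 3.6.1 keeps summaries and listings of AEs and serious AEs, including those requiring dose adjustment or delay, and of AEs of special interest.

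**Protocol.** Section 10.5.3.3 planned, for hematology among other panels, a "frequency table for newly occurring on-treatment CTCAE Grade 3 or 4 toxicities", shift tables from baseline to the worst on-treatment grade, and a graded listing. Table 6-3 (Section 6.2.1) gives dose rules for platelets, ANC, febrile neutropenia and hemoglobin. Under Section 8.1.1, abnormal laboratory values "constitute adverse events only if they induce clinical signs or symptoms, are considered clinically significant", need therapy, or require a change in study medication. Sections 7.2.2.5 and 8.1.2.1 add that a value requiring a dose hold must be reported as an AE.

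**The concern.** Low blood counts have their own dose-management table, and hematology is sampled repeatedly. The close-out SAP cancels the efficacy analyses, so safety is the main content left in the report. Yet the SAP both promises laboratory output and withdraws it, and a programmer cannot follow every sentence at once. If Sections 3.6.3 and 4 prevail, hematologic toxicity reaches the report only through AE records. Two indirect routes are closed as well: Section 4 drops concomitant-medication output, which would show transfusions and growth factors, and drops the reasons for dose interruption and reduction. The question is how much the AE tables still carry.

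**Working it through.** The plan states no figure on this point. The check sets the texts side by side and then classifies the counts.

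**Step 1: conflicts within the SAP**

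| Retained text | Conflicts with |
|---|---|
| 3.6: safety rests partly on out-of-range laboratory values | 3.6.3: nothing beyond liver tests is analyzed |
| 3.6: all safety assessments are listed | Section 4: no laboratory listings |
| 3: all raw data are listed | Section 4: no laboratory listings |
| Table 1-1: laboratory changes are a safety endpoint | 3.6.3 and Section 4 |
| 3.6.3: hepatic summary and listing are kept | Section 4: read literally, these are excluded too |

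**Step 2: which counts are AEs by definition**

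Table 6-3 has 3 counts × 4 grades = 12 rows, leaving febrile neutropenia aside. A row that requires interruption or discontinuation is an AE under protocol 7.2.2.5, 8.1.1 and 8.1.2.1.

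| Count | Dose action required | No dose action required |
|---|---|---|
| Platelets | grades 2, 3, 4 | grade 1 |
| ANC | grades 3, 4 | grades 1, 2 |
| Hemoglobin | grades 3, 4 | grades 1, 2 |
| Total | 3 + 2 + 2 = 7 | 1 + 2 + 2 = 5 |

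All 6 grade 3-4 rows are in the first column. Both febrile neutropenia rows also require interruption or discontinuation. The 5 rows on the right become AEs only if symptomatic, treated or judged clinically significant.

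**Step 3: when a grade 3 ANC meets a planned dose**

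Table 7-1 schedules five hematology samples after the first dose through Cycle 3 Day 1. Dosing is 21 days on and 7 days off.

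| Sample | Position | Grade 3 ANC forces a hold? |
|---|---|---|
| C1D15 | planned doses remain in the cycle | yes |
| C1D21 | last dosing day | depends on when the result is known |
| C2D1 | 21 planned doses ahead | yes; 6.2.1 lets Day 1 be delayed |
| C2D21 | last dosing day | depends on when the result is known |
| C3D1 | 21 planned doses ahead | yes |

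So 3 of 5 force a hold and 2 of 5 can leave a gap. The Day 21 gap needs all of these:

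- The result arrives after the Day 21 dose. Protocol 7.2.2 calls for pre-dose assessment, so a result known in time would hold that dose.
- ANC is back to at least 1.0 × 10^9/L by the next Day 1. The break goes ahead as scheduled: "The planned 7-day break should begin on the originally planned date regardless of mid-cycle interruptions".
- It is a first occurrence. For that case Table 6-3 reads "Re-initiate study drug at the same dose level. If toxicity recurs at grade 3", so no dose level changes.
- There are no symptoms, no therapy and no judgement of clinical significance.

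The ±3-day window in protocol 7.1 means that a Day 21 sample can fall anywhere from Day 18 to Day 24. Days 18 to 20 leave doses to hold; Days 22 to 24 lie inside the break.

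**Step 4: what 10 patients can show**

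For zero events in n patients, the exact two-sided 95% upper limit is 1 − 0.025^(1/n).

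- n = 10: 31%
- n = 7: 41%
- n = 3: 71%

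The 7:3 split is an assumption; the documents do not give arm sizes. Any hematology table would be descriptive only.

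**The case against.** The omission is open and reasoned. Section 4 and the document history both state it and tie it to the halt at 10 patients and a named report format. ECG, vital signs, exposure and efficacy output are cut for the same reason, so restoring one item can look like a preference about the contents of a short report. AE tables with grade and dose action remain. The list of AEs of special interest is not shown and parts of Section 4 are redacted, so a neutropenia or myelosuppression grouping may exist.

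Much of this stands, and it rules out several stronger readings that a reader might infer:

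- *AE reporting cannot stand in for hematology data at all.* Protocol 7.2.2.5 and 8.1.2.1 make every count that triggers a hold an AE, so most grade 3-4 counts and grade 2 platelets should appear.
- *Such counts appear only if the investigator chooses to record them.* Where a hold is required, recording is mandatory.
- *Cycle 1 Day 15 is the only sample where a first grade 3 ANC must interrupt dosing.* Day 1 of Cycles 2 and 3 precedes 21 planned doses, so a hold applies there too.
- *All 10 patients lose data that matter.* The documents do not show how many had low counts that went unrecorded.

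The objection does not remove the conflicts in Step 1. A small sample is a reason to drop inference, but it does not explain why individual values cannot be listed. The SAP already makes an exception for liver tests, so the short format can carry one. A special-interest grouping would not help with values that were never recorded as AEs, because it is built from AE records.

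**Conclusion.** The concern holds in limited form and is worth acting on. The SAP contradicts itself on laboratory output, and if its deletions prevail, no hematology value is tabulated or listed as laboratory data. AE tables should carry most grade 3-4 counts and grade 2 platelets. They need not carry ANC or hemoglobin at grades 1-2, platelets at grade 1, shifts from baseline, time course, or the narrow Day 21 case, which can arise at 2 of the 5 scheduled samples examined. The number of missing values cannot be derived. This is a disclosed limit on reporting, not a concealed one. The conclusion assumes that the AE rules in protocol 7.2.2.5, 8.1.1 and 8.1.2.1 are applied as written and that no redacted text restores hematology output.

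**What to change.** In SAP 3.6.3, replace the closing sentence with text to this effect: *ANC, platelets and hemoglobin will be listed by patient with CTCAE 4.03 grade, cycle and day. A descriptive shift table from baseline to the worst single on-treatment grade will be given by treatment.*

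- Use the reporting groups in SAP 3 (a) to (c) for the listing, and (a) and (b) for the table, in line with the existing rule that summary tables cover only those two.
- State that the worst single value is used. Otherwise the averaging default in SAP 3, or the rule in 2.1.2.8 that picks the assessment nearest the planned day, could hide it.
- Reconcile SAP 3, 3.6, 3.6.3 and Section 4, so that Section 4 exempts both the hematology output and the hepatic output that it now appears to exclude.

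No dose or clinical rule changes. The data are already collected, so the cost is SAP wording, one listing and one standard table on 10 patients. The downside is a slightly longer report that departs from its template, with output that supports description only.
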